The PRAC initiated a subsequent benefit-risk evaluation and considered that the controlled clinical studies required by the Note for guidance on clinical investigation of medicinal products for treatment of nociceptive pain (CPMP/EWP/612/00, issued 21 November 2002) for long-term treatment of chronic pain are not available for flupirtine-containing medicinal products². Based on the fact of observed liver effects recorded during long-treatment with Flupirtine and on the absence of controlled long-term clinical studies, the PRAC noted that the management of chronic pain is no longer favourable in terms of the benefit-risk balance for flupirtine-containing medicinal products. The PRAC adopted a recommendation on 13 June 2013 under the provisions of article 107i of Directive 2001/83/EC³.

Taking the currently available data into account, the PRAC decided that the benefit-risk balance for flupirtine-containing products is favourable in the treatment of acute pain, subject to implementation of the following risk minimisation measures⁴:

- Limitation of indication to acute pain in adults if treatment with other analgesics (e.g. NSAIDs, weak opioids) is contraindicated.
- Restriction of Flupirtine use to a maximum of two weeks of treatment.
- Contraindication of Flupirtine in patients with pre-existing liver disease or alcohol abuse.
- Contraindication of Flupirtine in patients concomitantly taking other medications which are known to cause Drug Induced Liver Injury (DILI).

- Weekly liver function tests during treatment and discontinuation in the case of abnormal liver function tests or clinical symptoms.

The PRAC imposed a DHPC, which was distributed on 15 July 2013, in order to communicate the outcome of the PRAC/EMA decision to healthcare professionals⁵. The SmPCs for flupirtine-containing medicinal products have been revised accordingly by Lupin in February 2014 and MAHS marketing flupirtine-containing medicinal products in September/October 2013⁶. The educational material was distributed in February 2015.

Patients and prescribers have been provided with joint educational material according to the PRAC request, prepared jointly by all German MAHs. The educational material, the DUS and a PASS protocol are parts of the RMP.

As of 5 September 2013, the European Commission implemented the decision (C(2013) 5788 final) with the majority opinion of the CMD(h) addressed to all member states based on the PRAC's recommendation⁷.

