9.7.2.2 Flupirtine exposure

Flupirtine exposure will be defined as one or more prescriptions of Flupirtine. These prescriptions will be identified using the ATC code for Flupirtine or INN. The Flupirtine exposure start date (i.e. the cohort entry date) for each patient will be defined as the date of the first record of Flupirtine prescription during each of the defined twelve-month patient selection window.

Treatment duration

The treatment duration (in days) will be evaluated by using the recommended treatment duration by the physician. If this is not available, the treatment duration cannot be determined exactly as the dose recommendation “as required (pro re nata)” is very often given in the therapy of acute pain. Therefore, the percentage of patients with no information according to recommendation by the physician will be determined.

Prescription length

The prescription length (in days) will be determined as follows:

- For prescriptions with available information on recommended dose per day: from the prescription date plus the expected number of days of drug supply based on the package size and the recommended daily dose
- For all prescriptions without recommendation of dosage: from the prescription date plus the expected number of days of drug supply based on the package size and the DDD(400 mg / day)

The prescription length is therefore not necessarily identical to the treatment duration.

The following parameters will be considered in the analysis for each Flupirtine prescription:

- Date of prescription
- Recommended daily dose by physician
- Recommended treatment duration by physician

Analyses:

- Number and percentage of patients with prescriptions of a flupirtine-containing medicinal product during the 12-month patient selection window
- Treatment duration in days
- Prescription length
- Single use and repeated use

Treatment episodes

A treatment episode will be defined as one or more prescriptions (repeated prescriptions) of flupirtine with gaps between prescription length not more than 7 days. In the case the gap between the prescriptions is longer than 7 days it will be considered as two subsequent treatment episodes. The analysis of treatment episodes will consider prescription length based on DDD, because for all prescriptions this information will be available.

Analyses:

- Number and percentage of episodes
- Min, max, mean, median length of episodes
- Patients within each episode

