9.7.2.4 Comparison of the patient/prescriptions of the two observational periods

The comparison of the patients/prescriptions of the two observational periods (assessment period and reference period) based on IMS[®] Disease Analyzer data will consider the following parameters. The comparisons will be performed separately by physician panel and will be stratified by incident and prevalent users:

- Number and percentage of patients with any diagnosis of disease contraindicated for NSAIDs or weak opioids
- Number and percentage of prescriptions with diagnosis associated with acute pain
- Number and percentage of patients with single and repeated flupirtine prescriptions within the defined time period
- Number and percentage of prescriptions with LFT monitoring during flupirtine treatment
- Length of treatment episodes
- Number and percentage of patients with at least one treatment episode longer than 14 days (based on DDD)

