9.9. Limitations of the research methods

IMS[®] Disease Analyzer is representative of Germany as a whole insofar as that the included practices are selected to adequately reflect geographic coverage and differences between urban and rural locations. This database contains information from approximately 3,000 office-based physicians (including specialists) who represent approximately 2.4% of all practices in Germany. The balance of various specialties in the IMS[®] Disease Analyzer does not, however, exactly reflect the balance in Germany. The lack of data from Flupirtine-prescribing oncologists will limit only to some extent the representativeness of results. For the characterization and comparison of the prescribing practice, however, this does not pose a problem.

The limitations of the IMS[®] Disease Analyzer are those of a provider-sourced EMR database. Patients seeking care outside the EMR practice setting will not have that utilisation recorded in the database. One of the main reasons for data documentation is reimbursement purposes. In the IMS[®] Disease Analyzer patients cannot be tracked across panels. Therefore, patients cannot be followed up across specialties and double counting of patients cannot be completely ruled out when analyzing more than one panel. It is planned to use of the PCP and the orthopaedist panels for this study.

For patients covered in the IMS[®] Disease Analyzer the medical history of patients will be evaluated for at least 12 months.

The duration of Flupirtine treatment (in days) will be evaluated using the treatment duration recommended by the physician. In cases where this information is not available, the treatment duration will be calculated using recommended dosage by the physician. The dose recommendation “on demand (pro re nata)” is very often given in the therapy of acute pain, acute pain episodes, and acute pain exacerbations which occur repeatedly. Therefore, the actual treatment duration is often shorter compared to the length of prescription.

The length of prescription will be determined from the recommended daily dose by the physician (if available) or using the defined daily dose (DDD). The dose recommendation “on demand” will not be taken into account for the determination of prescription length.

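### For one-pack episodes, the compared share of patients with an episode over 14 days is decided by pack content alone, so a change between 2012 and 2014 cannot be read as shorter treatment without a split

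*Protocol*

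**What the plan says.** Protocol section 7 lists among the risk minimisation measures "Restriction of Flupirtine use to a maximum of two weeks of treatment". Section 9.7.2.4 carries this limit into the before/after comparison as "Number and percentage of patients with at least one treatment episode longer than 14 days (based on DDD".

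Section 9.7.2.2 fixes how the length is obtained:
- An episode is "one or more prescriptions (repeated prescriptions) of flupirtine with gaps between prescription length not more than 7 days", so a single prescription is enough.
- "The analysis of treatment episodes will consider prescription length based on DDD, because for all prescriptions this information will be available". The DDD therefore applies even where the physician recorded a daily dose.
- The DDD rule gives the "expected number of days of drug supply based on the package size and the DDD(400 mg / day".

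Section 9.9 adds that on-demand advice is very frequent in acute pain and "will not be taken into account for the determination of prescription length". It concludes: "Therefore, the actual treatment duration is often shorter compared to the length of prescription".

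Section 9.7.1 intends the period comparison to be looked at for the effect of the risk minimisation measures and names treatment duration as its example.

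**The concern.** The 14-day percentage looks like a measure of how many patients exceed the two-week limit. For an episode made of one pack it records only whether the pack holds more than 14 DDDs. It contains no information on how long that patient took the drug.

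The plan counts such patients together with those for whom a further prescription shows that supply was renewed. It is the only percentage in section 9.7.2.4 set at the two-week limit. The other duration item there, length of treatment episodes, rests on the same DDD basis. If the mix of pack sizes or strengths differed between 2012 and 2014, the percentage could move without any change in treatment length, and a reader could credit or blame the label change for it. If the mix was stable, a real change would look smaller than it was.

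**Working it through.** The protocol gives no expected value for this parameter, so there is no stated figure to reproduce. The check applies its own rule.

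**Inputs from the protocol.** DDD 400 mg per day and one prescription per episode sufficing (9.7.2.2); threshold over 14 days (9.7.2.4); strengths of 400 mg and 100 mg both on the market (Annex 3, list i). Pack sizes are not given.

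**Switch point.** Days = units x strength / 400, flagged if above 14.
- 14 x 400 mg = 5,600 mg; 5,600 / 400 = 14 units; 5,600 / 100 = 56 units.
- 15 units of 400 mg give 15 days and are flagged; 14 give 14 days and are not.
- 57 units of 100 mg give 14.25 days and are flagged; 56 give 14 days and are not.

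**Strength alone changes the result** (unit count assumed). 20 x 400 / 400 = 20 days, flagged. 20 x 100 / 400 = 5 days, not flagged.

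**The error runs both ways** (unit counts and daily intakes assumed, for arithmetic only).
- 20 x 400 mg = 8,000 mg; at 600 mg per day it lasts 13.3 days, yet it is flagged at 20 days.
- 50 x 100 mg = 5,000 mg; at 300 mg per day it lasts 16.7 days, yet it is not flagged at 12.5 days.

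**Effect on the comparison** (illustration). Let q be the true share treated over 14 days, all assumed flagged, and s the share of the remaining patients whose pack holds more than 14 DDDs. Flagged share = q + (1 - q) x s. Neither q nor s is in the protocol.

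Pack mix shifts, treatment length unchanged:
- q = 10%, s from 70% to 40%: 0.10 + 0.90 x 0.70 = 73%, then 0.10 + 0.90 x 0.40 = 46%, a fall of 27 points.
- q = 30%, same shift: 0.30 + 0.70 x 0.70 = 79%, then 0.30 + 0.70 x 0.40 = 58%, a fall of 21 points.

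Pack mix stable, true share falls from 30% to 10%: the visible change is -20 x (1 - s) points.

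| s | Visible change (points) |
|---|---|
| 0% | -20 |
| 30% | -14 |
| 50% | -10 |
| 70% | -6 |
| 90% | -2 |

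**Sampling error for scale.** Table 2 reproduces: 11,284 x 0.75 = 8,463 and 1,821 x 0.75 = 1,365.75 (stated 1,365). With the rounded sizes of 8,400 and 1,300 per period, the 95% half-width of a difference at p = 0.5 is 1.96 x sqrt(2 x 0.25 / n), that is 1.5 and 3.8 points. Intervals within the incident and prevalent strata will be wider. A large sample does not remove the distortion.

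**The case against.** The strongest reply has four parts.

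- **The aim is prescribing, not intake.** Sections 8 and 9.1 speak of prescribing practices and patterns. Prescribing more than 14 DDDs is prescriber behaviour, and a move to smaller packs may be a genuine response to the restriction. This stands, and is why the planned row should be kept. It does not license reading the row as treatment length, which section 9.7.1 invites.
- **The weakness is disclosed.** The row is labelled as DDD-based, and sections 9.7.2.2 and 9.9 both separate prescription length from treatment duration. That is so, but the measure still enters the comparison unaltered.
- **Related information is planned.** Single versus repeated prescriptions are compared, and physician-recommended duration is tabulated with the percentage missing. But the first is not crossed with the 14-day flag, and the second is not in the section 9.7.2.4 list.
- **Extra rows belong in the analysis plan.** Layout does. The DDD basis and the 14-day parameter are fixed in the protocol itself.

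A reader might infer that the planned percentage is a strict upper bound on the true share. The documents do not support that: section 9.9 says shorter often, not always; intake below the DDD lengthens treatment; and care outside the practice or in another panel is not recorded.

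A reader might also take the time from first to last prescription in an episode as a strict lower bound, and trust any change on which the two measures agree. That fails too:
- A 12-DDD pack on day 0 and a repeat on day 16 leave a gap of 4 days and form one episode, though on-demand use could make them two short courses.
- With prescriptions on days 0 and 25, 20-DDD packs leave a gap of 5 days and give one episode counted by both measures. 10-DDD packs leave a gap of 15 days and give two 10-day episodes counted by neither.

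Pack mix alone can thus move both measures in the same direction.

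**Conclusion.** The point holds as a disclosed but uncorrected weakness of measurement. For one-pack episodes the 14-day flag is exactly a flag for more than 5,600 mg in the pack. Given what section 9.9 says about on-demand use, it probably overstates long treatment in that group, with some error in the other direction.

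The size is unknown. It depends on how many flagged patients have a one-prescription episode and on whether pack size or strength shifted between 2012 and 2014, and the protocol reports neither. The 27-point and 21-point movements above show what is possible under assumed values; they are not estimates. The documents do not show that such a shift occurred. With a stable mix the illustration gives a distorted level and a diluted change, not a false change.

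**What to change.** 1. Keep the planned row, described as a measure of the amount prescribed.
2. Split it in each period into patients flagged only through a one-prescription episode and patients whose flagged episode was continued by a further prescription. The second group is not free of pack content, because DDD supply still joins prescriptions, but it rests on evidence of renewal.
3. Tabulate pack content (14 DDDs or less versus more) and strength by period.
4. Add to section 9.7.2.4 the share with physician-recommended duration over 14 days among prescriptions where it is recorded, with the percentage missing. Use recorded durations only: sections 9.7.2.2 and 9.9 differ on what is done when none is recorded and should be reconciled.
5. Optionally add a row on the time from first to last prescription in the episode, as a sensitivity check and not as a bound.
6. State in advance that a change confined to one-prescription episodes will not be attributed to shorter treatment.

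All of this uses variables the protocol already lists. The cost is a few table rows and a less simple headline.

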9.8. Quality control

Data quality control is conducted at several levels.

At database level:

The quality unit of the IMS production department continuously verifies the quality of its numerous panels in terms of panel representativeness, consistency of collected data, and validation of coding of physicians' verbatim.

At study level:

All parts of the study from protocol development to the reporting of results are conducted according to IMS SOPs.

Data for analysis will be extracted by a programmer with extensive programming and analysis experience with the LifeLink EMR data.

The following steps will be undertaken to ensure quality and accuracy of all programming developed during the course of the study:

- Methodology Review: the statistical analysis plan and accompanying table shells will be reviewed and approved by senior staff at the IMS team.
- Programming Code Review: all programming code will be developed by a senior programmer with extensive programming and analysis experience with the LifeLink EMR data.
- Statistical Review: all results tables produced during the study will be reviewed by senior staff member of the COE Pharmacoepidemiology and Drug Safety at IMS.

9.9. Limitations of the research methods

IMS[®] Disease Analyzer is representative of Germany as a whole insofar as that the included practices are selected to adequately reflect geographic coverage and differences between urban and rural locations. This database contains information from approximately 3,000 office-based physicians (including specialists) who represent approximately 2.4% of all practices in Germany. The balance of various specialties in the IMS[®] Disease Analyzer does not, however, exactly reflect the balance in Germany. The lack of data from Flupirtine-prescribing oncologists will limit only to some extent the representativeness of results. For the characterization and comparison of the prescribing practice, however, this does not pose a problem.

The limitations of the IMS[®] Disease Analyzer are those of a provider-sourced EMR database. Patients seeking care outside the EMR practice setting will not have that utilisation recorded in the database. One of the main reasons for data documentation is reimbursement purposes. In the IMS[®] Disease Analyzer patients cannot be tracked across panels. Therefore, patients cannot be followed up across specialties and double counting of patients cannot be completely ruled out when analyzing more than one panel. It is planned to use of the PCP and the orthopaedist panels for this study.

For patients covered in the IMS[®] Disease Analyzer the medical history of patients will be evaluated for at least 12 months.

The duration of Flupirtine treatment (in days) will be evaluated using the treatment duration recommended by the physician. In cases where this information is not available, the treatment duration will be calculated using recommended dosage by the physician. The dose recommendation “on demand (pro re nata)” is very often given in the therapy of acute pain, acute pain episodes, and acute pain exacerbations which occur repeatedly. Therefore, the actual treatment duration is often shorter compared to the length of prescription.

The length of prescription will be determined from the recommended daily dose by the physician (if available) or using the defined daily dose (DDD). The dose recommendation “on demand” will not be taken into account for the determination of prescription length.

9.10. Other aspects

None

10. Protection of human subjects

This study is non-interventional and based on secondary data use. No identifying data is collected in any of selected databases. These databases are set up following local law, including data privacy regulation.

Ethics Committee/Institutional Review Board approval is not necessary.

The study will follow the Guidelines for Good Pharmacoepidemiology Practices (GPP) of the International Society for Pharmacoepidemiology (ISPE) 2007 and be in accordance with Guide on Methodological Standards in Pharmacoepidemiology of the European Network of Centres for Pharmacoepidemiology and Pharmacovigilance (ENCePP).^{13,14}

The study will comply with the definition of non-interventional (observational) studies provided in the Article 2(c) of Directive 2001/20/EC (definition of non-interventional/observational studies).¹⁵ The study will follow the Guideline on Good Pharmacovigilance Practice (GVP): Module VIII – Post-Authorisation Safety Studies (EMA 2012, Revision 2013) and the ICH harmonised tripartite guideline Pharmacovigilance Planning E2E (ICH 2004) referring to the nature of non-interventional observational studies.^{16,17}

11. Management and reporting of adverse events (AEs) / adverse reactions (ADRs)

Not applicable, as the study will be carried out by secondary use of already collected data.

According to the current guidelines of the International Society for Pharmacoepidemiology (ISPE) (2007, Section VI) and the EMA Guideline on Good Pharmacovigilance Practices (GVP): Module VI – Management and Reporting of Adverse Reactions to Medicinal Products (EMA, 2012b, Section VI:C.1.2.1), non-interventional studies which are based on secondary use of data do not require reporting of adverse events¹⁸.

12. Plans for disseminating and communicating study results

The study will be registered in the EU-PAS register (currently the ENCePP e-register of studies).

The study report will be written in English, using the template included in the GVP Module VIII “Guidance for the format and content of the final study report of non-interventional post-authorisation safety studies” (EMA/623947/2012)¹⁹. When reporting results of this study, the appropriate STROBE checklist (von Elm, 2007) will be followed²⁰.

The final study report will be communicated to BfArM.

Annex 1. List of stand-alone documents

Number	Document reference number	Date	Title
1-DHPC	Not applicable	July 2013	Direct Healthcare Professional Communication (DHPC): Einschränkungen der therapeutischen Zielgruppe und Begrenzung der Behandlungsdauer für Flupirtine-haltige Arzneimittel nach Bewertung des LebertoxizitätsrisikosText
2-Updated SmPC	Not applicable	July2014	Summary of Product Characteristics Flupirtinmaleat-Hormosan 100mg Hartkapseln, Dated July2014

Annex 2. ENCePP checklist for study protocols

Doc.Ref. EMA/540136/2009

ENCePP Checklist for Study Protocols (Revision 2, amended)

Adopted by the ENCePP Steering Group on 14/01/2013

The [European Network of Centres for Pharmacoepidemiology and Pharmacovigilance \(ENCePP\)](#) welcomes innovative designs and new methods of research. This Checklist has been developed by ENCePP to stimulate consideration of important principles when designing and writing a pharmacoepidemiological or pharmacovigilance study protocol. The Checklist is intended to promote the quality of such studies, not their uniformity. The user is also referred to the [ENCePP Guide on Methodological Standards in Pharmacoepidemiology](#) which reviews and gives direct electronic access to guidance for research in pharmacoepidemiology and pharmacovigilance.

For each question of the Checklist, the investigator should indicate whether or not it has been addressed in the study protocol. If the answer is "Yes", the page number(s) of the protocol where this issue has been discussed should be specified. It is possible that some questions do not apply to a particular study (for example in the case of an innovative study design). In this case, the answer 'N/A' (Not Applicable) can be checked and the "Comments" field included for each section should be used to explain why. The "Comments" field can also be used to elaborate on a "No" answer.

This Checklist should be included as an Annex by marketing authorisation holders when submitting the protocol of a non-interventional post-authorisation safety study (PASS) to a regulatory authority (see the [Guidance on the format and content of the protocol of non-interventional post-authorisation safety studies](#)). Note, the Checklist is a supporting document and does not replace the format of the protocol for PASS as recommended in the Guidance and Module VIII of the Good pharmacovigilance practices (GVP).

Study title:

Drug utilisation study (DUS) on flupirtine-containing medicinal products

Study reference number:

Section 1: Milestones	Yes	No	N/A	Page Number(s)
